		11.2.1 Source Documents	
		11.2.2 DATA COLLECTION	
	11.3	ETHICS COMMITTEE (EC) AND COMPETENT AUTHORITY (CA) APP	
			55
		DEVICE ACCOUNTABILITY	
12.	PUBLICA	ATION POLICY	56
13.	Biblio	GRAPHY	57

1. Primary Study Contacts

SPONSOR FARAPULSE, Inc.

[name]

CLINICAL RESEARCH

ORGANIZATION

MedPass International SAS

[name]

LEGAL REPRESENTATIVE MedPass Limited

[name]

[name] – United Kingdom

2. Executive Summary

SPONSOR NAME: FARAPULSE, Inc.

TITLE OF TRIAL: "IMPACT"

PROTOCOL NUMBER:

CS0172-02, Revision D, VERSION 02 (FR)

OBJECTIVE: The objective of the safety and feasibility trial is to

demonstrate that the creation of electrically isolating lesions via pulsed electric field (PEF) ablation applied using the FARAPULSE Cardiac Ablation System during concomitant heart surgery is feasible and a safe treatment

for paroxysmal atrial fibrillation (AF).

CLINICAL Creation of electrically isolating lesions in cardiac tissue via ablation using the FARAPULSE Cardiac Ablation

System during concomitant heart surgery is a feasible and

safe treatment for paroxysmal AF.

NAME OF FARAPULSE Cardiac Ablation System

INVESTIGATIONAL

• iowaPulse Cardiac Ablation Catheter System

DEVICE: • iowaStar Generator System

DESIGN: Prospective, single-arm, multi-center feasibility trial.

STUDY Subjects will be consented to undergo surgical PEF
POPULATION ablation using the FARAPULSE Cardiac Ablation

System concomitant to heart surgery.

PLANNED Up to 25 subjects

ENROLLMENT:

CLINICAL SITES: Up to 3 clinical sites in Europe

DURATION OF Subjects will be followed at 30 days, 3 months, 6 months and 12 months following the index surgical procedure with

and 12 months following the index surgical procedure with a blanking period for recurrent atrial fibrillation or atrial tachycardia of 3 months following the index surgical

procedure.

The enrollment period is estimated to take 6 months and subjects will be followed for up to 12 months for a total

duration of approximately 18 months.

PRIMARY SAFETY ENDPOINT:

A composite safety endpoint consisting of the proportion of subjects that experience one or more of the following serious adverse events (SAEs) related to the investigational procedure and/or device within 30 days of the PEF ablation procedure or hospital discharge, whichever is later, except as noted below:

- Cardiac death

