The risks and complications associated with thermal or non-thermal cardiac ablation depend on the complexity of the procedure. The most common complications due to cardiac ablations include bleeding, cardiac tamponade, stroke/TIA, pulmonary vein stenosis, phrenic nerve injury, thromboembolism, air embolism, post-procedural arrhythmias, and vascular complications. Further, recurrences of atrial fibrillation (AF) or atrial tachycardia after an initial AF catheter ablation procedure (20 – 40% of patients**xxix*) are common.

Gelsomino 2014^{xl} noted in a study of SAEs (Serious Adverse Event) rates for studies of convergent AF ablation (N=335) (Table 1). There were 3 early deaths (0.9%) and three conversions to sternotomy and cardiopulmonary bypass (0.9%). There were no late deaths or thromboembolic events. These SAE rates include both catheter ablation and epicardial ablation procedures in the reviewed studies. Expected adverse event rates from an isolated epicardial procedure are likely to be lower.

Table 1: Data from Gelsomino 2014 – Adverse Event Rates for Epicardial Ablation

Event	Frequency (%)
Bleeding	6 (1.8%)
Tamponade	4 (1.2%)
Pleural effusion	1 (0.3%)
Hemothorax	1 (0.3%)
Pneumothorax	1 (0.3%)
Pneumonia	1 (0.3%)

In conclusion, risks related to the FARAPULSE Cardiac Ablation System are expected to be no different from those of the products approved and available on the market for concomitant open-heart surgery, ablation procedures. FARAPULSE will be conducting bench and in-vivo testing to ensure safe use of the device during clinical investigation and ultimately compliance with Directive 93/42/EEC. FARAPULSE will also ensure, through its Risk Management System, that the residual and controllable risks have been minimized or eliminated.

4. Investigational Device

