5.4 Trial Endpoints

5.4.1 Primary Safety Endpoint

A composite safety endpoint consisting of the proportion of subjects that experience one or more of the following serious adverse events (SAEs) related to the investigational procedure and/or device within 30 days of the PEF ablation procedure or hospital discharge, whichever is later, except as noted below:

- Cardiac death
- Stroke and/or transient ischemic attack (TIA)

- Myocardial infarction (MI)
- Excessive bleeding
- Atrio-esophageal fistula
- Persistent post-surgical phrenic nerve paralysis at 12 months
- Severe pulmonary vein stenosis (>70%)

Table 3 summarized the primary safety endpoint definitions.

Table 3: Primary Safety Endpoint Definitions

able 3: Primary Safety Endpoint Definitions					
Potential Serious					
Adverse Event	Definition				
Cardiac Death	Excludes all non-cardiac deaths.				
Stroke	A new focal neurological deficit of presumed vascular origin persisting more than 24 hours and with a neuro-imaging study that does not indicate a different etiology. All patients suspected of having a stroke will be evaluated by a neurologist and have appropriate imaging tests performed (CT or MRI) as determined by a neurologist.				
	 The 24-hour criterion is excluded if the subject undergoes cerebrovascular surgery or dies during the first 24 hours. 				
	This stroke definition includes subjects presenting with clinical signs and symptoms suggestive of subarachnoid hemorrhage, intracerebral hemorrhage, or cerebral infarction.				
	Stroke events in cases of blood disorders such as leukemia, and strokes secondary to trauma are excluded.				
Transient Ischemic Attack (TIA)	A focal ischemic neurological deficit of abrupt onset and of presumed vascular etiology that resolves completely within 24 hours of onset. All patients suspected of having a TIA will be evaluated by a neurologist and have appropriate imaging tests performed (CT or MRI) as determined by a neurologist.				

Potential Serious Adverse Event	Definition
Myocardial Infarction* (MI)	The presence of any one of the following criteria: 1) detection of ECG changes indicative of new ischemia (new ST-T changes or new LBBB), which persist for more than one hour; 2) development of new pathological Q waves on an ECG; 3) imaging evidence of new loss of viable myocardium or new regional wall motion abnormality.

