Excessive Bleeding*	Bleeding requiring re-operation or 2 units of PRBC transfusion within any 24 hours of the first 7 days following the index procedure.
Atrioesophageal Fistula	An atrial esophageal fistula is defined as a connection between the atrium and the lumen of the esophagus. Evidence supporting this diagnosis includes documentation of esophageal erosion combined with evidence of a fistulous connection to the atrium such as air emboli, an embolic event, or direct observation at the time of surgical repair. A CT scan or MRI scan are the most common methods of documentation of an atrial esophageal fistula.
Phrenic Nerve Paralysis*	Absent phrenic nerve function as assessed by a sniff test. A phrenic nerve paralysis is defined as permanent if it persists for 12 months or longer following ablation.
Pulmonary Vein Stenosis*	A reduction of the diameter of a PV or first generation PV branch. PV stenosis can be categorized as mild <50%, moderate 50%-70%, and severe ≥70% based on the percentage reduction in the diameter of the PV or PV branch. A severe PV stenosis should be considered a major complication of AF ablation.

^{* 2012} HRS/EHRA/ECAS Expert Consensus Statement on Catheter and Surgical Ablation of Atrial Fibrillation: Recommendations for Patient Selection, Procedural Techniques, Patient Management and Follow-up, Definitions, Endpoints, and Research Trial Design.

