6.1.1 Potential Adverse Events

The following anticipated events have been identified as possible complications of cardiac surgery and atrial fibrillation ablation procedures and these and others may be associated with the FARAPULSE Cardiac Ablation System:

- Air embolism
- Anemia
- Arrhythmia, potentially requiring cardioversion
- Arteriovenous fistulae
- Arrhythmias, possibly requiring a pacemaker
- Drug allergic reaction or side effects (e.g., from contrast, steroids, analgesics, anesthetics, anticoagulants, sedatives, etc.)
- Back pain
- Bed sores
- Bleeding, hematoma, hemorrhage or aneurysm at vascular access sites
- Coronary artery or vein injury
- Cardiac tamponade
- Cardiac arrest or cardiac failure
- Catheter entrapment
- Cardiogenic shock
- Congestive Heart failure
- Coupling across/crossing of unintended structures
- Death
- Esophageal injury
- Hemorrhage
- Hemodynamic compromise
- Hemopericardium
- Hemoperitoneum
- Hemothorax
- Hypotension
- Increased defibrillation threshold

- Local infection, systemic infection, and/or sepsis
- Myocardial infarction / transient ischemia
- Nerve damage
- Organ failure
- Pain
- Perforation (e.g., of diaphragm, heart, liver, lung, and/or vessels).
- Pericardial irritation
- Pericardial effusion
- Pericarditis
- Peritonitis
- Pneumomediastinum
- Pneumopericardium
- Pneumoperitoneum
- Pneumothorax
- Risk of cancer or birth defect/harm to fetus from x-ray exposure
- Skin burns/irritation from x-ray exposure
- Stroke/transient ischemic attack
- Surgical or open-heart surgery to remove retained catheter
- Thrombosis
- Thromboembolism
- Vessel damage, dissection, or occlusion.
- Phrenic nerve injury
- Conduction system injury resulting in sinus arrest or heart block, either transient or permanent

Concomitant medicinal and surgical treatments used during the procedure and follow-up phase of the clinical study include structural heart surgery for the index procedure, anticoagulation, and antiarrhythmic therapy. The FARAPULSE Cardiac Ablation System does not have any known interactions with these therapies.

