7.7 Assessment of Safety

7.7.1 Primary Safety Endpoint

A composite safety endpoint consisting of the proportion of subjects that experience one or more of the following serious adverse events (SAEs) related to the investigational procedure and/or device within 30 days of the PEF ablation procedure or hospital discharge, whichever is later, except as noted below:

- Cardiac death
- Stroke and/or transient ischemic attack (TIA)
- Myocardial infarction (MI)
- Excessive bleeding or
- Atrio-esophageal fistula
- Persistent post-surgical phrenic nerve paralysis at 12 months
- Severe pulmonary vein stenosis

All adverse events (AEs) will be adjudicated for seriousness as well as device and procedure relatedness.

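### The primary safety composite is already limited to related SAEs, yet it still leaves out a related non-cardiac death that meets no other component

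*Combined protocol and SAP*

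**What the plan says.** The synopsis, section 5.4.1 and section 7.7.1 give the same seven components: cardiac death, stroke or TIA, myocardial infarction, excessive bleeding, atrio-esophageal fistula, phrenic nerve paralysis persisting at 12 months, and severe pulmonary vein stenosis. A listed SAE counts only if it is "related to the investigational procedure and/or device within 30 days of the PEF ablation procedure or hospital discharge, whichever is later", with exceptions noted in the list.

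Table 3 in 5.4.1 defines the components. The whole entry for Cardiac Death is "Excludes all non-cardiac deaths". The table's asterisk, which cites the 2012 consensus statement, is attached to myocardial infarction, bleeding, phrenic paralysis and vein stenosis. It is not attached to death, and no reason for the exclusion is given. The stroke row does provide for a fatal course: "The 24-hour criterion is excluded if the subject undergoes cerebrovascular surgery or dies during the first 24 hours". Excessive Bleeding is "Bleeding requiring re-operation or 2 units of PRBC transfusion within any 24 hours of the first 7 days following the index procedure".

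Section 6.1.1 lists possible complications of cardiac surgery and AF ablation together, among them "Local infection, systemic infection, and/or sepsis", "Organ failure" and cardiac tamponade. On adjudication, 7.7.1 states: "All adverse events (AEs) will be adjudicated for seriousness as well as device and procedure relatedness". Section 10.12 gives the CEC all procedure-related and serious events.

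**The concern.** Restricting death to cardiac causes normally keeps background mortality out of a device endpoint. Here the relatedness requirement already does that. The extra exclusion therefore acts only on deaths that have been judged related, which are the deaths a primary safety result should show.

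Section 7.2 calls this a first-in-man trial, section 5 sets out to demonstrate a safe treatment, and 7.1 says the results will inform the design of later studies. A headline proportion of 0% that coexists with a related death would mislead readers who take only the primary result. The secondary safety endpoint (5.4.2, 7.7.2) would include the death. However, it counts any SAE by interval from the operation onward, with no relatedness limit, so the death would be merged with all SAEs of the index surgery.

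There is a smaller parallel for tamponade. Section 3.4 names it as a common ablation complication, but it is not a component. It enters the composite only if it also meets another component, mainly Excessive Bleeding or Cardiac Death.

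**Working it through.** The plan has no calculated sample size, power or safety threshold (7.1, 7.2), so there is no figure of its own to reproduce. The check sets the definitions side by side and then computes what one omitted event does.

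**1. Which related deaths are counted.**
- Cardiac cause: counted as Cardiac Death.
- Through stroke: counted as Stroke, including death in the first 24 hours.
- Through atrio-esophageal fistula: counted as the fistula.
- Through bleeding with re-operation or 2 units in the stated period: counted as Excessive Bleeding.
- Non-cardiac, with no component met (for example sepsis or organ failure): not counted.

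Only the last line is a gap, and it is the same in the synopsis, 5.4.1 and 7.7.1.

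**2. Which related tamponades are counted.** One that needs re-operation for bleeding, reaches the transfusion threshold in the first 7 days, or ends in cardiac death is counted. One managed without re-operation and below that threshold is not. The bleeding definition does not make clear whether the 7-day limit also applies to re-operation. If it does, a later re-operated tamponade is also missed.

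**3. Effect of one omitted death.** Inputs: n = 25, the maximum in 5.5, taken as the denominator; no other subject with an event; Clopper-Pearson 95% intervals.
- Not counted: 0/25 = 0%. Upper limit 1 − 0.025^(1/25) = 13.7%. Interval 0 to 13.7%.
- Counted: 1/25 = 4.0%. Lower limit 1 − 0.975^(1/25) = 0.1%. The upper limit solves (1 − p)^25 + 25p(1 − p)^24 = 0.025, giving p = 20.4%. Interval 0.1 to 20.4%.

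Each omitted subject lowers the primary proportion by 1/25 = 4.0 percentage points.

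**4. Frequency.** The review cited in 3.4 reports 3 early deaths in 335 (3/335 = 0.9%) without cause or relatedness. Table 1 gives 4 tamponades in 335 (4/335 = 1.2%) without relatedness, treatment or overlap with bleeding. Neither yields a rate of omitted events.

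**The case against.** The strongest case for leaving the plan alone is that this is a consistent design choice with no decision attached. The list is the same wherever it appears, the analysis is descriptive, and no stopping rule or threshold uses the composite. The residual is narrow: the death must be related, non-cardiac, inside the window and free of any qualifying component. Nor would it be lost. It would be recorded with its outcome and relationship to the device (8.2), adjudicated by a CEC that can pause or terminate the study (10.12), and included in the secondary endpoint. All of this stands and limits the weight of the point. It does not explain why a related death should be absent from the primary safety figure, and no separate table of related deaths is promised.

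A second objection also stands. Section 6.1.1 lists sepsis and organ failure jointly for heart surgery and ablation. Section 8.1 assigns events whose relatedness cannot be assessed to the possible level, and 5.4.1 does not say which levels count as related. An unqualified change to related death of any cause could bring deaths from the index operation into the composite. The fix has to deal with this.

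Three stronger readings are tempting, and the documents do not support them.
- A reader might infer that every non-cardiac death drops out. It does not: related deaths through stroke, fistula or qualifying bleeding count through those components.
- A reader might infer that tamponade must become a component because 3.4 says "The most common complications due to cardiac ablations include bleeding, cardiac tamponade, stroke/TIA, pulmonary vein stenosis, phrenic nerve injury". The same sentence goes on to thromboembolism, air embolism, arrhythmias and vascular complications, which are not components by name either. Being named there is not enough, and many tamponades would count as Excessive Bleeding.
- A reader might size the gap from the cited tamponade rate: 1 − (1 − 4/335)^25 = 26% for at least one in 25 subjects. That is any tamponade, in convergent procedures. The related and uncounted shares are unknown. Section 3.4 expects lower rates for an isolated epicardial procedure, but this trial combines on-pump surgery with transseptal mapping, so even the direction of the difference is unknown.

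**Conclusion.** The point holds for death. Given the relatedness filter, the exclusion in Table 3 can remove only related deaths, and a related non-cardiac death meeting no other component leaves the primary safety result unchanged. The size per subject is 4.0 percentage points: 0/25 (0 to 13.7%) instead of 1/25 (4.0%, 0.1 to 20.4%), assuming the full 25 subjects and no other event. The frequency cannot be estimated from the documents.

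For tamponade, only a reporting gap is shown: a related case below the Excessive Bleeding definition is not visible in the primary result. That supports an extra line in the tables, not a new component.

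What is affected is how the primary result reads and how it is used in planning later studies. Error rates, power and decision rules are not affected, because the plan has none for this endpoint. The change is worth making because it is cheap.

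**What to change.** - **Preferred.** In the synopsis, 5.4.1, Table 3 and 7.7.1, replace cardiac death with CEC-adjudicated death of any cause related to the PEF ablation procedure or the device, in the existing window. State which causality levels in 8.1 count as related, so that deaths due only to the index heart surgery are not brought in.
- **If the definition is not amended.** Report the number of subjects with a related death of any cause beside the composite, with an exact 95% interval.
- **Secondary reporting line only.** Show subjects with a related serious cardiac tamponade in the same window beside the composite. List separately any that occur at the 3-month remapping (5.13.5), which uses transseptal puncture and falls outside the window unless discharge was later. The CEC should write down its definition of tamponade before it reviews events.

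No new assessments are needed, since events are already adjudicated for seriousness and relatedness. Changing the definition needs a protocol amendment and, if it falls under 11.3, ethics committee and competent authority approval. The reporting options cost a few table lines and a short definition. For the definition change, the downside is a possibly higher headline event rate, by an amount that cannot be given in advance.

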5.4.2 Secondary Safety Endpoint

The proportion of subjects reporting one or more SAEs for each follow-up interval. The intervals will include the period from:

- The surgical procedure for the surgical PEF ablation through the Day 30 follow-up visit;
- The Day 30 follow-up visit through the Month 3 follow-up visit;

- The Month 3 follow-up visit through the Month 6 follow-up visit; and
- The Month 6 follow-up visit through the Month 12 follow-up visit.

5.4.3 Primary Feasibility Endpoint

Proportion of subjects that achieve procedural success. Procedural success is defined as the creation of an electrically isolating "box" lesion encompassing the pulmonary veins and posterior left atrium using the study device. Specifically, the ability of the device to create a contiguous line of electrical block in the specified region of the left atrium.

5.4.4 Secondary Feasibility Endpoints

The secondary feasibility endpoint(s) include:

Proportion of subjects that achieve long-term technical success. Long-term technical success is defined as electrical isolation of the pulmonary veins and posterior left atrium assessed at a follow-up electro-anatomical remapping procedure performed 3-months post index procedure.

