5.13.3 Pre-Discharge

Prior to hospital discharge the following data will be collected:

- Use, changes in or discontinuation of anticoagulation, rate control and/or antiarrhythmic medications;
- Cardioversion(s) since surgery;
- For subjects on warfarin, assessment of INR therapeutic levels (maintain as clinically indicated);
- For subjects on dabigatran, perform a PTT and, if required, a thrombin time (Section 4.7.2.7 Anticoagulation Regimen);

- Cardiac rhythm as determined by a 12-lead ECG on day of hospital discharge;
- Heart failure status as assessed by NYHA classification on day of hospital discharge; and Adverse Events.

5.13.4 1 Month Follow-Up

Discharged subjects will return for an office visit 30 days (± 7 days) postablation treatment. Subjects that continue to be hospitalized 30 days postablation will have their 30-Day Follow-Up assessment performed at discharge. At a minimum, the following data will be collected at 30 Day Follow-Up visit:

- Use, changes in or discontinuation of anticoagulation, rate control and/or antiarrhythmic medications;
- Cardioversions since last visit;
- For subjects on anticoagulants, assessment of INR/PTT therapeutic levels (maintain as clinically indicated):
- Cardiac rhythm as determined by a 12-lead ECG at the time of the visit;
- Heart failure status as assessed by NYHA classification at the time of visit;
- Any hospital readmissions, including admission and discharge dates, since discharge from the original procedure; and

5.13.5 3 Month Follow-Up

Subjects will return for an office visit at the end of the blanking period (90 days \pm 14 days post-ablation treatment). During the blanking period, any recurrence of AF will be documented; however, recurrences of AF, AFL or AT during this time will not be considered therapeutic treatment failures. Subjects are not permitted to undergo repeat ablation during the blanking period. If a repeat ablation procedure is performed during this time, the subjects will be considered a therapeutic treatment failure and exited from the study.

At a minimum, the following data will be collected at the end of the blanking period follow-up visit:

- Use, changes in or discontinuation of anticoagulation, rate control and/or antiarrhythmic medications;
- Cardioversions since last visit;
- Any additional ablation procedures performed;
- For subjects on anticoagulants, assessment of INR/PTT therapeutic levels (maintain as clinically indicated);

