- Cardiac rhythm as determined by a 12-lead ECG at the time of the visit;
- Heart failure status as assessed by NYHA classification at the time of visit;
- Any hospital readmissions, including admission and discharge dates, since the previous visit; and
- Adverse events.
- If a subject is symptomatic for AF at the end of the blanking period, an event monitor will be provided to be used up to the 6-month follow-up visit to capture AF episodes.
- Patients will undergo an electro-anatomical remapping procedure to assess electrical isolation of the posterior left atrium and pulmonary veins. Any electrical gaps may be closed at the investigator's discretion using a commercially approved ablation device. This will consist of placement of catheters in the left atrium via femoral access and transeptal puncture using conventional electrophysiology techniques.
- Patients will undergo a cardiac CT or MRI scan at 3 months to assess the patency of the pulmonary veins.

5.13.6 6 Month Follow-up

Subjects will return for an office visit 6 months (180 days \pm 30 days) postablation treatment. At a minimum, the following data will be collected at 6 months:

- Use, changes in or discontinuation of anticoagulation, rate control and/or antiarrhythmic medications;
- Cardioversions since last visit;
- · Any additional ablation procedures performed;
- For subjects on anticoagulants, assessment of INR/PTT therapeutic levels (maintain as clinically indicated);
- Cardiac rhythm as determined by a 12-lead ECG at the time of the visit;
- Heart failure status as assessed by NYHA classification at the time of visit;
- Cardiac rhythm as determined by a 24-hour continuous ECG monitor following the visit for subjects in NSR at the time of the visit;
- Any hospital readmissions, including admission and discharge dates, since the previous visit; and
- Adverse events.

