There is no plan within this protocol to combine an endovascular ablative procedure with epicardial ablation using the FARAPULSE Cardiac Ablation System. However, if ablation using the FARAPULSE Cardiac Ablation System were ineffective and atrial fibrillation recurred, further ablative therapy may be pursued by the patient's physician outside the context of this study. When further ablation is done with electro-anatomical mapping, a further ablation procedure would not introduce any risks over and above those already inherent in a second ablation procedure whether done through the epicardium or the endocardium. The risks of any second ablative procedure are the same as the risks summarized above.

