7.4 Imputation for Missing Data

Imputations for missing data in (e.g., withdrawn subjects, loss to follow-up, missing data) will not be performed. Analyses will be performed with all available data only.

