7.6.2 Secondary Feasibility Endpoint

The secondary feasibility endpoint(s) include:

Proportion of subjects that achieve long-term technical success. Long-term technical success is defined as electrical isolation of the pulmonary veins and posterior left atrium assessed at a follow-up electro-anatomical remapping procedure performed 3-months post index procedure.

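### Long-term technical success has no study-device condition and no rule for subjects ablated with another device, so likely device failures can drop out of the durability rate

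*Combined protocol and SAP*

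**What the plan says.** The primary feasibility endpoint (5.4.3) credits a box lesion "encompassing the pulmonary veins and posterior left atrium using the study device". The secondary feasibility endpoint has no such condition. Section 5.4.4 and the statistical section 7.6.2 use the same sentence: "Long-term technical success is defined as electrical isolation of the pulmonary veins and posterior left atrium assessed at a follow-up electro-anatomical remapping procedure performed" three months after the index procedure.

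Three other places bear on how a subject is scored:

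- Section 5.13.5, on the blanking period: "Subjects are not permitted to undergo repeat ablation during the blanking period". It then provides for the case all the same: "If a repeat ablation procedure is performed during this time, the subjects will be considered a therapeutic treatment failure and exited from the study".
- Section 5.13.5, on the remap itself: "Any electrical gaps may be closed at the investigator's discretion using a commercially approved ablation device".
- Section 7.4 rules out imputation: "Analyses will be performed with all available data only".

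Section 5.4.5 makes repeat ablation a failure, but only for therapeutic success. No section states the technical-success status of a subject who was ablated with another device.

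**The concern.** The endpoint is meant to show whether the lesion made by the study device lasts. As worded, it records whether the region is isolated at three months, whatever produced the isolation, among subjects who have a remap. Subjects in whom the lesion failed early and led to another ablation are the ones most likely to have no remap.

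In the assessment schedule (Table 4), three months is the only follow-up visit with electro-anatomical mapping, so this rate is the trial's only planned direct measure of durability. Section 7.1 says the results will be used to design further studies. An inflated rate would carry over into their assumptions.

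**Working it through.** The plan states no expected rate, interval or sample-size calculation for this endpoint, so there is no figure to reproduce. The check is a reading of the rules followed by an illustration.

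**Following the rules for a subject ablated with another device**

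1. *Re-ablated during blanking.* Section 5.13.5 makes the subject a therapeutic failure and exits the subject from the study. There is then normally no study remap. Section 7.4 uses available data only, so the subject is in neither the numerator nor the denominator of 5.4.4. The same subject counts as a failure for therapeutic success under 5.4.5.
2. *Gaps closed at the remap.* Section 5.13.5 allows this with a commercial device. Section 5.4.4 does not say whether isolation is read before or after closure.
3. *Another surgical device at the index operation.* No section mentions it. Section 6.1.1 says "There is no plan within this protocol to combine an endovascular ablative procedure with epicardial ablation", and treats later ablation for recurrent AF as outside the study. Neither statement covers a second surgical device on the day. If it happened, the subject would fail 5.4.3 but meet the wording of 5.4.4 if isolated at three months. The procedural data listed in 5.13.2 contain no item that would identify such a subject.

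**Size of the first route**

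Inputs: N = 25 (the maximum in 5.5). Assumed, not in the documents: *s* subjects isolated by the study device at the remap, *k* subjects exited after re-ablation, and a remap for everyone else.

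- Rate under the present rules: s/(N − k)
- Rate with re-ablated subjects counted as not isolated: s/N
- Difference: s·k / [N(N − k)]

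With s = 18 and k = 2: 18/23 = 78.3% against 18/25 = 72.0%. The difference is 36/575 = 6.3 points.

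With s = 20:

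| k | Exited, available data | Counted as not isolated | Difference |
|---|---|---|---|
| 1 | 20/24 = 83.3% | 20/25 = 80.0% | 3.3 points |
| 2 | 20/23 = 87.0% | 20/25 = 80.0% | 7.0 points |
| 3 | 20/22 = 90.9% | 20/25 = 80.0% | 10.9 points |

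For k = 2 the exact 95% intervals are 66.4% to 97.2% (20/23) and 59.3% to 93.2% (20/25). If the two subjects had instead been counted as successes, the rate would be 22/25 = 88.0%. Leaving them out therefore raises the rate almost as much: 7.0 against 8.0 points.

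**Size of the other two routes**

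Each subject wrongly scored as isolated adds 1/25 = 4 points. The documents give no basis for the number of such subjects, and it may be zero.

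**Direction**

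The upward bias requires that re-ablated subjects were less often isolated by the study lesion than the others. In the case s = 18, k = 2, if both re-ablated subjects in fact had intact study lesions, the true rate would be 20/25 = 80.0%, and 78.3% would be 1.7 points too low. Since re-ablation would usually follow a suspected failure, the upward direction is the likely one.

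**The case against.** A reader might infer that isolation produced by another device before the remap counts as a success of the study device. The documents do not say this. For ablation after the index operation they point the other way: 5.13.5 does not permit it in the blanking period and exits any subject who has it. The bias on that route comes from exclusion, not from a false success.

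A reader might also infer that a surgeon could simply finish a failed box with another device and have it credited. The wording would allow the credit, but the scenario is not planned or described. Section 5.13.2 refers the workflow to separate documents that are not part of this one. Section 5.13.7.2 describes a map made through femoral and transseptal access without saying when it is done relative to chest closure. Section 10.17 requires the sponsor's prior approval for deviations outside emergencies.

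It can further be said that the study is descriptive, that the primary feasibility endpoint keeps the device condition, and that 7.1 bases device performance on a per-protocol analysis that might exclude these subjects. The first two limit the consequences. The third does not help: the per-protocol set is not defined, excluding these subjects would again remove likely failures, and the intent-to-treat analysis uses the same endpoint wording and the same missing-data rule.

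Finally, the natural reading of a remap is that isolation is assessed first and gaps are closed afterwards. That is probably what is meant, but it is not written.

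**Conclusion.** The gap is real and modest. Long-term technical success lacks the device condition of the primary feasibility endpoint and has no scoring rule for other ablation. The firmest consequence follows from applying the plan as written: the exit rule in 5.13.5 and the available-data rule in 7.4 together take likely device failures out of the durability denominator.

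The illustrations give an overstatement of about 3 to 11 points for one to three such subjects among 25, and none if there are no such subjects. These counts are assumptions. So is the premise that re-ablated subjects had lost, or never had, isolation from the study lesion. Scoring after gap closure and credit for a second device at the index operation are openings in the wording, and the documents do not show that either will occur.

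**What to change.** In 5.4.4 and 7.6.2:

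- Define success as isolation at the three-month remap attributable to the study device alone, scored before any gap closure.
- Count as not isolated any subject who had non-study ablation of the pulmonary vein or posterior left atrial region between the index procedure and the remap, including subjects exited under 5.13.5.
- Report how many subjects had no remap, and why.

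Add one CRF item recording non-study ablation at the index procedure. Section 5.4.5 needs no change.

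The cost is a few lines of endpoint wording and one data item, and clinical care is unaffected. The reported rate may be slightly lower, and a subject re-ablated although the study lesion was intact would be scored conservatively. Limiting the rule to the target region avoids failing subjects for an unrelated left atrial lesion.
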